4.13.3 Clinical Laboratory Evaluation

Blood samples for hematology and clinical chemistry will be collected. Profiles for the hematology, clinical chemistry will be summarized, and patients with values outside the normal range during the on-treatment period during the study will be summarized.

Change from baseline for each of the hematology, clinical chemistry will be derived for each of the post-dose time points using the pre-dose measurement as the baseline. Descriptive statistics for the measurement at baseline and the measurement and change from baseline at each postdose time point will be tabulated.

Laboratory results recorded as " $< x$ " or " $\leq x$ " will be imputed as x ; results recorded as " $> x$ " or " $\geq x$ " will be imputed as x and a footnote will be added to indicate the number of patients and visits that were above the limit.

Each laboratory parameter will be classified as low, normal or high relative to the central laboratory’s normal range. For each treatment group shift tables will be generated from the predose category to the category post-dose for each laboratory parameter. The shift tables will present the number (percent) of patients who started in a category (low, normal, high) at baseline and ended in a category at each scheduled visit before the end of the study. A missing category will be included for both pre-dose and post-dose, so that all patients in the Safety population will

be represented in the table. The missing category includes the cases where the normal range is partially or completely missing, the unit of measurement is missing, and/or the laboratory result itself is missing. The percentages will be calculated using number of patients in the Safety population who have measurements at pre-dose and post-dose.

Shift tables comparing pre-dose to the other time points in the study may be generated if warranted after data review.

4.13.4 Vital Signs

Extreme vital signs will be determined using the following criteria:

- Heart rate either < 50 bpm or > 100 bpm,
- Systolic blood pressure either ≤ 90 mmHg or ≥ 160 mmHg,
- Diastolic blood pressure either ≤ 50 mmHg or ≥ 100 mmHg.

The number (percent) of patients having extreme vital signs will be tabulated by treatment group at each scheduled visit. The percentage will be calculated using the number of patients in the Safety population with data at each visit as the denominator. The number (percent) of patients having extreme vital signs post-baseline (including unscheduled assessments) will be calculated.

Change from baseline statistics will also be defined for the measurements of blood pressure, heart rate and temperature using the pre-dose values as baseline. Descriptive statistics for the measurement of temperature will also be provided by treatment group.

All patients who have an extreme vital sign value will be documented in a by-patient listing. The listing will include all of the vital sign measurements from the study for the patient, and the extreme values will be flagged.

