Randomization will be stratified by age group (<65 years and \geq 65 years), sex and site.

Secondary efficacy analyses will assess secondary endpoints as well as analyses of relevant subgroups.

Safety analyses will include assessments of adverse events, vital signs, electrocardiograms and laboratory parameters.

An independent Data Monitoring Committee will be used to monitor unblinded safety data.

2. Schedule of Activities

Table 2-1. Schedule of Activities

Study Day	S ^a	Treatment						Completion or Hospital Discharge or ED ^{b,c}	Follow-Up Phone Visit 1 ^d	Follow-Up Phone Visit 2 ^d
	≤1	1	2	7	15	16	21	28 (or the day discharged from hospital or ED)	42 ^d	60
Window Period (days)		-	-	±2	-	-	±2	±1	±2	±2
Eligibility review	X									
Informed consent	X									
Demographics	X									
Medical history ^e	X									
Height	X									
Weight	X							X		
Physical examination (directed unless otherwise noted)	X (complete)	X		X	X		X	X (complete)		
Vital signs ^f	X	← Every day from Day 1 to 27 → Predose and postdose on Days 1 and 15						X		
Hematology and clinical chemistry		X (pre-dose) ^g	X	X	X (pre-dose)	X	X	X		
COVID-19 panel ^h		X (pre-dose)	X	X		X	X	X		
Influenza/RSV/respiratory viral panel ⁱ		X								
Thyroid function test (TSH and FT4)		X (pre-dose)						X		
Pregnancy Test ^j	X (serum / urine)							X (urine)		
12-Lead ECG ^k		X (pre-and post-dose) ^l			X (pre-and post-dose)			X		

	S ^a	Treatment						Completion or Hospital Discharge or ED ^{b,c}	Follow-Up Phone Visit 1 ^d	Follow-Up Phone Visit 2 ^d
Study Day	≤1	1	2	7	15	16	21	28 (or the day discharged from hospital or ED)	42 ^d	60
Window Period (days)		-	-	±2	-	-	±2	±1	±2	±2
Randomization ^m		Within 24 hours of screening								
Study drug administration ⁿ		Within 8 hours of randomization			X					
SpO ₂ , O ₂ flow rate ^o	X	← Every day from Day 1 to 27 →						X		
NIAID ordinal assessment ^p	X	← Every day from Day 1 to 27 →						X	X	X
Adverse event monitoring ^q		← Every day from Day 1 to 27 →						X	X	X
Supportive pulmonary care ^r		← Every day from Day 1 to 27 →						X		
Concomitant medications ^s		← Every day from Day 1 to 27 →						X		

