Abbreviations: ECG = electrocardiogram; ECMO = extracorporeal membrane oxygenation; ED = early discontinuation; fT4 = free thyroxine; FU = follow-up; h = hours; ICF = informed consent form; IMV = intermittent mandatory ventilation; NIAID = National Institute of Allergy and Infectious Diseases; PK = pharmacokinetic; S = Screening; SO₂ = oxygen saturation; TSH = thyroid stimulating hormone.

- a Any procedure done as a standard of care 1 calendar day prior to ICF may be used as the screening procedure. Screening and Day 1 may occur on the same day.
- b Patients who are discharged from the hospital will complete the Completion or Hospital Discharge visit procedures
- c Patients who discontinue the study prior to study completion will complete the ED visit procedures.
- d Follow-up phone visit 1 should be conducted at 14 days after completion or hospital discharge or early discontinuation, or 28 days after the first dose of study drug, whichever occurs later. Follow-up phone visit 2 should be conducted at 60 days after first dose of study drug.
- e Ensure the onset of illness symptoms are captured, examples include fever, coughing, extreme fatigue, headache, myalgia.
- f Includes respiration rate, heart rate, temperature, and blood pressure. Vital signs need to be recorded once at approximately the same time each day. Post dose vital signs on Days 1 and 15 should be collected at the end of infusion and at approximately 1 hr after end of infusion.
- g If procedures were performed within 1 calendar day prior to infusion as part of standard of care and prior to ICF, that may be used as the sample collection on Day 1.
- h Data should be collected from local COVID19 panel laboratory pre-dose within 1 calendar day ≤Day 1, between 24 and 48 hr postdose on Day 2, and Day 16; and at any time on Days 7, 21, and 28 (or discharge or ED). Collection on Days 16 and 21 to be performed only if a Day 15 dose of study treatment was administered ([Appendix 2](#)).

- i Viral testing is only performed for patients who have undetermined or negative COVID-19 test(s). Viral testing is per the institution's testing guidelines.
- j For pregnancy test, only for women of child-bearing potential.
- k Single 12-lead ECGs will be obtained in the supine position at all indicated timepoints. On Days 1 and 15, ECGs will be collected pre-dose and at the end of infusion.

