13. Have undergone major surgery within 28 days prior to randomization or central venous access device placement for another pre-existing condition within 7 days prior to receiving first dose of study drug
14. Have liver cirrhosis with a Child-Pugh class B or worse or cirrhosis (any degree) and a history of hepatic encephalopathy or clinically meaningful ascites resulting from cirrhosis. Clinically meaningful ascites is defined as ascites resulting from cirrhosis and requiring ongoing treatment with diuretics and/or paracentesis.
15. Have a history of hypertensive crisis or hypertensive encephalopathy or current poorly controlled hypertension (systolic BP ≥ 160 mm Hg and/or diastolic BP ≥ 95 mm Hg) despite standard medical management.
16. Are concurrently enrolled in any other type of medical research judged not to be scientifically or medically compatible with this study.
17. Female patients who are pregnant and/or lactating.
18. Are investigator site personnel directly affiliated with this study and/or their immediate families. Immediate family is defined as a spouse, parent, child, or sibling, whether biological or legally adopted.
19. Are Lilly employees or are employees of any third-party involved in the study who require exclusion of their employees.

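### SAP 4.13.4 defines extreme vital signs by absolute level alone, so Table 23's any-time count is not treatment-emergent; a row tied to the pre-dose value should be added

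*SAP*

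**What the plan says.** SAP 4.13.4 sets fixed limits: heart rate below 50 or above 100 bpm; "Systolic blood pressure either ≤ 90 mmHg or ≥ 160 mmHg"; "Diastolic blood pressure either ≤ 50 mmHg or ≥ 100 mmHg". Two counts follow. One "will be tabulated by treatment group at each scheduled visit", with patients who have data at that visit as denominator. The other covers the whole post-baseline period: "The number (percent) of patients having extreme vital signs post-baseline (including unscheduled assessments) will be calculated". Neither refers to the patient's pre-dose value.

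The same section plans change from baseline for blood pressure, heart rate and temperature (Table 22, by study day), and a listing of all vital signs for every flagged patient.

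On frequency, the protocol's Schedule of Activities has vital signs "Every day from Day 1 to 27", and its footnote adds: "Vital signs need to be recorded once at approximately the same time each day". Days 1 and 15 have two post-dose readings each, at the end of infusion and about one hour later. Protocol 9.4.2 expects far more frequent monitoring in routine care.

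At entry, Protocol 6.2 criterion 15 excludes "current poorly controlled hypertension (systolic BP ≥ 160 mm Hg and/or diastolic BP ≥ 95 mm Hg) despite standard medical management".

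**The concern.** Elsewhere the SAP compares with the pre-dose state. An adverse event must be new or worse than baseline (4.13.2), and laboratory values get shift tables from the pre-dose category (4.13.3). The extreme vital-sign counts have no such rule, although patients admitted with pneumonia may well have a raised heart rate or blood pressure before the first infusion.

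The any-time count also depends on how often a patient is measured. Readings stop at discharge, shorter hospital stay is a study objective, and unscheduled values are included. A longer-staying or sicker arm can therefore collect more flags with no effect of the drug on vital signs. Randomisation does not remove this, because the difference arises after it.

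Table 23 is the only listed by-arm count of extreme values. Vital signs are not among the DMC tables in SAP 4.16, and Protocol 9.2.1 exempts tachycardia and bradycardia from SAE reporting unless judged drug-related. A count that mixes pre-existing, chance and new values is harder to read than it need be.

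**Working it through.** There is no figure in the plan to reproduce: the documents give no expected flag rate and no mean or SD for blood pressure or heart rate. Everything below rests on assumed inputs.

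**Inputs from the documents.** The limits above; one scheduled reading a day plus the post-infusion readings, so about 2 + 26 + 2 + 1 = 31 post-baseline readings for a full 28-day stay; 100 patients per arm.

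**Assumed model.** Patient mean μ ~ N(m, sb); independent readings around μ with SD s; an entry reading below 160; no drug effect. Then p = 1 − Φ((160 − μ)/s), and the flag rate over k readings is the average of 1 − (1 − p)^k.

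**Step 1: growth with the number of readings** (m = 130, sb = 12, s = 10).

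| k | 1 | 7 | 10 | 14 | 28 |
|---|---|---|---|---|---|
| any SBP ≥160 | 2.1% | 9.7% | 12.1% | 14.6% | 20.6% |

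With varying stay (mean about 10 readings) and SDs 12/8 to 15/14, the rate is about 6–24%. On a wider grid (m 120–135, sb 10–15, s 8–12, k 7–32) it is about 0.5–47%. Correlation between days lowers it a little.

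**Step 2: already beyond the limit before dosing.**
- Systolic: about 1–5% (1.3% at SDs 12/8, 4.2% at 15/12). Without the entry filter it would be 1 − Φ(30/√(12² + 8²)) = 1 − Φ(2.08) = 1.9%, up to 1 − Φ(30/√(15² + 14²)) = 1 − Φ(1.46) = 7.2%.
- Heart rate, mean 85, between-patient SD 12, daily SD 6 or 10: 1 − Φ(15/√(12² + 6²)) = 1 − Φ(1.12) = 13%; 1 − Φ(15/√(12² + 10²)) = 1 − Φ(0.96) = 17%. About 29–48% would be flagged at some time, and 31–40% of those flags come from patients already above 100 pre-dose.

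**Step 3: effect of stay alone.** Mean stays of 8 and 11 days give 18% and 21% flagged (16% and 19% in a second simulation). The standard error of the first difference is √((0.18×0.82 + 0.21×0.79)/100) = 0.056, so the shift is about half a standard error. The per-visit rate does not accumulate: on Day 7 it is 4.2% in both.

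**Step 4: is a treatment difference lost?** Power = Φ(difference/SE − 1.645), one-sided 0.05, 100 per arm, m = 130, SDs 12/10, k = 10, uniform rise of 5 mmHg.

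| Measure | No effect → +5 mmHg | Power |
|---|---|---|
| current flag | 12.1% → 21.5% | 56% |
| flag plus rise ≥20 | 6.9% → 14.8% | 56% |
| flag on two consecutive readings | 2.1% → 5.3% | 33% |
| change from baseline, one day (SD 14.0) | 5 mmHg | 81% |

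First row: SE = √((0.121×0.879 + 0.215×0.785)/100) = 0.0525; 0.094/0.0525 − 1.645 = 0.15; Φ = 0.56. Last row: SE = 14.0×√(2/100) = 1.98; 5/1.98 − 1.645 = 0.88; Φ = 0.81. For a uniform 10 mmHg rise the current flag has 99%.

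If instead 10% of patients have a sustained 30 mmHg rise (SDs 12/10, varying stay), simulated power is 42% for the current flag and 56% for a row requiring a non-extreme pre-dose value and a rise of at least 20 mmHg.

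**The case against.** The strongest reply is that the plan already covers this. Change from baseline by study day is tabulated, the per-visit count does not accumulate with stay, flagged patients are listed in full, and clinically significant findings that lead to a diagnosis are reported as adverse events (Protocol 9.4.2), which are tabulated by arm. Table 23 is descriptive, so power for it is not a planned property. All of this stands and limits the point to reporting. It does not make the any-time count treatment-emergent, and mean change is not built to show large rises in a few patients.

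Three stronger readings are tempting, and the documents do not support them.

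- A reader might infer that noise hides a blood-pressure effect. Chance flags fall on both arms and dilute the contrast. Under the assumed inputs the current flag still has 94–98% power for a uniform 10 mmHg shift with varying stay.
- A reader might infer from the shared value of 160 that Table 23 mainly counts patients who entered near the limit. The match is systolic only (diastolic is 95 at entry and 100 for the flag), and heart rate has no entry limit. Criterion 15 describes poorly controlled hypertension despite management, so it is not a single-reading filter. In simulation only 33–45% of flagged patients had a pre-dose value of 150 or more.
- A reader might infer that two consecutive daily readings should be required. That helps for a large sustained rise in a minority (54–68%, against 28–42% for the current flag, for 30 mmHg in 10% of patients). It loses power for uniform shifts and would drop transient changes after infusion, which the schedule is designed to capture. Power computed for responders defined as meeting such a rule favours it by construction.

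**Conclusion.** The point holds as a modest reporting weakness. Table 23's any-time count is not treatment-emergent, includes patients beyond a limit before dosing, and rises with the number of readings. The text alone establishes this. The sizes (about 6–24% flagged for systolic pressure, 1–5% already beyond 160, 13–17% already above 100 bpm) depend on assumed means and SDs and could be well outside these ranges. Heart rate is where the missing pre-dose condition matters most. The effect on a between-arm comparison is dilution, and no efficacy conclusion depends on it.

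**What to change.** Keep the limits, both existing counts, Table 22 and the listing. Add to SAP 4.13.4 and Table 23 a by-arm treatment-emergent row for each parameter and direction:

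- not beyond the limit at the last pre-dose value; and
- beyond it at any scheduled post-baseline reading, post-infusion readings included, with a pre-specified minimum change in the same direction (for example ≥20 mmHg systolic, ≥10 mmHg diastolic, ≥15 bpm);
- denominator: patients not beyond that limit pre-dose.

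Do not require two consecutive daily readings for this row. Read it beside the per-visit counts, because it still accumulates with stay (at m = 130, SDs 12/10, the flag with a rise of ≥20 mmHg goes from 6.9% at 10 readings to 13.7% at 28). Using scheduled readings only removes the part due to extra monitoring.

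The cost is SAP wording and one more row per parameter, with no new data. The change thresholds are a convention and should be fixed before unblinding.

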4.13.5 Electrocardiograms

The number (percent) of patients who had an abnormal ("Abnormal, CS" or "Abnormal, NCS") ECG at any time while on-treatment will be tabulated by treatment group. All on-treatment ECGs, including unscheduled assessments, will be considered.

4.14 Subgroup Analyses

The primary end point will be analyzed for the following subgroups:

- Patients who are confirmed SARS-CoV-2 positive and otherwise o age group < 65 and ≥ 65 o sex o BMI < 30 and ≥ 30 o Patients that receive one dose and two doses of study drug o Patients who reach NIAID ordinal scale score = 2 within day 4 and those who do not o Patients with baseline NIAID ordinal scale score of 3, and those with baseline score of 4 or 5
- Patients who received remdesivir and those who do not.

For endpoints which do not consider mortality, subgroup analyses of survivors only may be conducted if appropriate.

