
 To evaluate survival without the need for IMV/ECMO in patients treated with LY3127804 	
 Proportion of patients who are alive and respiratory failure free (i.e. never having required mechanical ventilatory support) by Day 28

 To evaluate mortality rate during treatment with LY3127804 	
 Death within 28 days from first dose of study drug

 To evaluate reduction in hospital stay during treatment with LY3127804 	
 Length of hospitalization

 To evaluate safety of LY3127804 	
 AEs and SAEs

Abbreviations: AE = adverse event; ECMO = extracorporeal membrane oxygenation; IMV= intermittent mandatory ventilation; NIAID = National Institute of Allergy and Infectious Diseases; SAE = serious adverse event; SpO₂ = oxygen saturation

Summary of Study Design:

Study I7W-MC-UDAA (UDAA) is a multicenter, randomized, double-blind, parallel, placebo-controlled study in patients who are hospitalized for pneumonia and presumed or confirmed COVID-19.

Treatment Arms and Duration:

LY3127804 20 mg/kg or placebo administered intravenously (IV) on Days 1 and 15. If patients are discharged from the hospital prior to day 15, they will not receive a second dose and will undergo Completion or Hospital Discharge visit procedures.

Number of Patients:

Approximately 210 patients will be enrolled so that 200 patients complete the study, for an estimated total of 100 evaluable patients per treatment group. A sample size of 100 in each group will have 81% power to detect a difference between the placebo group and the LY3127804 group using a Wilcoxon rank-sum test with a 0.05 one-sided significance level.

Statistical Analysis:

The Wilcoxon rank-sum analysis of the primary endpoint, days free of mechanical ventilation within 28 days among survivors, will use a scoring scheme where a higher score is a better patient outcome. We will assign a score of -1 to patients who die before 28 days. For those patients who survive to Day 28 the score will be equal to the number of ventilator free days (VFDs) calculated according to the above definition. The statistical method for this endpoint will be based on the van Elteren test adjusting for the randomization stratification factors.

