6.2. Exclusion Criteria

Patients will be excluded from study enrollment if they meet any of the following criteria at screening, until specified otherwise:

1. Have ARDS and/or require immediate intermittent mandatory ventilation (IMV).
2. In the opinion of the investigator, is moribund irrespective of the provision of treatments.
3. Any concurrent serious medical condition (e.g. patients with estimated glomerular filtration rate [eGFR] < 15 mL/min/1.73m² or on dialysis, preexisting lung disease requiring O₂ at rest, a body mass index [BMI] that precludes techniques such as proning) or concomitant medication that in the opinion of the investigator that would preclude participation in the study.
4. Have received treatment with a drug predominantly targeting Ang2 activity (e.g., tyrosine kinase inhibitors and/or antibody treatment) within the past month or 5 half-lives, whichever is longer.
5. Have a known sensitivity to mAbs or other therapeutic proteins, to agents of similar biologic composition as LY3127804, or to any products used in the formulation of LY3127804 (refer to the IB for LY3127804 for details) or are incompatible with the treatment of LY3127804.

6. Have a known history or show evidence of human immunodeficiency virus (HIV) and/or hepatitis A, B or C
7. Exclusion Criterion [7] has been deleted.
8. Have a significant bleeding disorder or active vasculitis or had a Grade ≥ 3 bleeding episode within 12 weeks prior to receiving treatment
9. Have experienced any arterial thromboembolic event, including myocardial infarction, unstable angina, cerebrovascular accident, or transient ischemic attack, within 6 months prior to receiving treatment
10. Have experienced any Grade 3 or 4 venous thromboembolic event that is considered by the investigator to be life-threatening or that is symptomatic and not adequately treated by anticoagulation therapy within 6 months prior to receiving treatment. Patients with chronic portal vein thrombosis who are asymptomatic and not considered to need anticoagulation therapy are eligible.
11. Have chronic congestive heart failure (New York Heart Association class ≥ 3) or uncontrolled cardiac dysrhythmia
12. Have a serious nonhealing: (a) wound, (b) peptic ulcer, or (c) bone fracture, within 28 days prior to receiving first dose of study drug

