7.1. Treatments Administered

This study involves a comparison of LY3127804 20 mg/kg administered intravenously once every two weeks to placebo. The investigator may withhold the second dose (refer to Section 8.1). Table 7-1 shows the treatment regimens.

Table 7-1. Treatment Regimens

Regimen	Dose Day 1	Dose Day 15
LY3127804	20 mg/kg	20 mg/kg
Placebo	Matching placebo	Matching placebo

Note: Patients weighing 150 kg and above will receive a maximum LY3127804 dose of 3000 mg. Please see the Pharmacy Manual for further instructions.

LY3127804 will be administered as a slow IV infusion over at least 90 (± 15) minutes. Infusion duration may be increased or stopped as deemed necessary based on the institutional standard of care. If an infusion reaction is observed, the patient should be treated according to instructions in Section 9.2.2. Resuscitation equipment and emergency drugs must be available at all times when the patient is being infused. Patients should be observed for at least 60 minutes after completion of the infusion. The actual start and stop time of infusion will be recorded.

The investigator or his/her designee is responsible for the following:

- explaining the correct use of the investigational agent(s) to the site personnel
- verifying that instructions are followed properly
- maintaining accurate records of investigational product infusion and collection
- at the end of the study returning all unused medication to Lilly, or its designee, unless the sponsor and sites have agreed all unused medication is to be destroyed by the site, as allowed by local law.

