7.7. Concomitant Therapy

All concomitant therapies that are part of routine care are allowed and can be used during the study. If indicated, anticoagulation therapies, including full-dose anticoagulation therapies, are allowed.

All concomitant therapies must be recorded in the eCRF.

Concomitant medications captured should include unapproved (“off-label”) medication, such as, for example, convalescent antibodies, remdesivir, chloroquine, hydroxychloroquine, and IL-6 antagonists.

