4.12.3.2 NIAID Ordinal Assessment

The NIAID will be assessed daily and defined as the lowest score achieved for that day.

The scoring is based on the clinical status of the patient as described below.

NIAID Score	Description
1	Death

2	Hospitalized, on invasive mechanical ventilation or extracorporeal membrane oxygenation (ECMO)
3	Hospitalized, on non-invasive ventilation or high flow oxygen devices
4	Hospitalized, requiring supplemental oxygen
5	Hospitalized, not requiring supplemental oxygen - requiring ongoing medical care (COVID-19 related or otherwise)
6	Hospitalized, not requiring supplemental oxygen - no longer requires ongoing medical care
7	Not hospitalized, limitation on activities and/or requiring home oxygen
8	Not hospitalized, no limitations on activities

The lowest value from Day 1 through Day 28 for a patient on the NIAID ordinal scale will be analyzed using the van Elteren test adjusting for the randomization stratification factors. The number need to treat (NNT) to prevent one patient from progressing to level 2 or 1 will be calculated. Mean values will be calculated and differences in treatment effect estimates at Days 7, 14 and 28 will be analyzed. Mean value by treatment group will be plotted over time.

[figure not shown]
Time to the first 2-point improvement on the NIAID scale will be analyzed between treatment groups. The time for subjects who did not achieve 2-point improvement will be censored at day 28 and stratification will be ignored in this analysis. A Kaplan-Meier plot with log-rank test will be used to compare treatment groups.

The stacked bar plot(s) representing the proportion of subjects in each score by treatment arm over time will be generated with stratification ignored. An example of such plot is as follows. The details of the score will be included in the footnote of the plot.

In addition to the stacked bar plot based on the original NIAID scores, another stacked bar plot that lumps NIAID scores into four categories will be generated. The four new categories are:

- a. Death (NIAID score = 1),
- b. IMV/ECMO (NIAID score = 2),
- c. Requiring O₂ or medical care (NIAID scores = 3, 4, 5), and
- d. Not requiring O₂ nor medical care (NIAID scores = 6, 7, 8).

Figure 2.0 Example of a Stacked Bar Plot:

4.12.3.3 28-day Mortality

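### SAP 4.14 splits ventilator-free days by doses received, by NIAID 2 within Day 4 and by remdesivir use, none of them limited to baseline

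*SAP*

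**What the plan says.** SAP 4.14 states that the primary endpoint will be analyzed in a list of subgroups. Three entries matter here:

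- "Patients that receive one dose and two doses of study drug" (Table 31 in SAP 5.1)
- "Patients who reach NIAID ordinal scale score = 2 within day 4 and those who do not" (Table 32)
- "Patients who received remdesivir and those who do not" (Table 34)

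The same list labels the NIAID 3 versus 4 or 5 split as baseline. These three carry no such label and no note on interpretation. The primary analysis in SAP 4.12.1 is a between-arm van Elteren test, and Protocol 10.3.5.1 describes these as subgroup analyses of the primary analysis. That section names only SARS-CoV-2 status, age group and sex, as examples. Tests default to one-sided 0.05 (SAP 4.1), with no multiplicity adjustment (SAP 4.6).

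**The concern.** A subgroup contrast between arms is a randomized comparison only if treatment cannot affect membership. Here it can.

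- **Doses.** The Protocol synopsis says: "If patients are discharged from the hospital prior to day 15, they will not receive a second dose". Protocol 7.1 adds: "The investigator may withhold the second dose". Protocol 8.1 also ends dosing for certain infusion reactions and bleeding events. Receiving two doses therefore depends on survival, continued hospital stay and tolerability up to Day 15. Shorter stay is itself a secondary objective (SAP 2.2).
- **NIAID 2 within Day 4.** Score 2 is invasive ventilation or ECMO (SAP 4.12.3.2). Patients who need immediate ventilation are excluded (Protocol 6.2), so the state arises after enrolment. Days on the ventilator are also what the endpoint counts.
- **Remdesivir.** Protocol 7.7 says: "All concomitant therapies that are part of routine care are allowed and can be used during the study". SAP 4.11 counts anything taken on or after the first dose as concomitant, and SAP 4.12.4.2 compares remdesivir use over Days 1-28 between arms as an outcome. The group can therefore include starts after dosing.

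A reader of Table 31 could infer an effect of the second dose, and a reader of Table 32 a too-late-to-treat effect, when the pattern is only selection.

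**Working it through.** **Inputs from the documents** (Protocol 10.1; SAP 3.2 and 4.12.1). Placebo: IMV 25%, death 12.5%. Both are halved on LY3127804. Mean difference 3.0 days; death scores -1; 100 per arm; one-sided 0.05; stated power 81%.

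**Assumed score models.** Alive and never ventilated scores 28.

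- *A*: all deaths follow IMV; ventilated survivors uniform 0-18 (mean 9). A ventilated patient averages 0.5 × (-1) + 0.5 × 9 = 4. Placebo 0.75 × 28 + 0.25 × 4 = 22.0; LY3127804 0.875 × 28 + 0.125 × 4 = 25.0; difference 3.0.
- *B*: 70% of deaths follow IMV; ventilated survivors uniform 0-26 (mean 13). Placebo -0.125 + 0.1625 × 13 + 0.7125 × 28 = 21.94; LY3127804 -0.0625 + 0.08125 × 13 + 0.85625 × 28 = 24.97; difference 3.0.

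**The plan's power.** Unstratified, tie-corrected rank-sum tests on 20,000 simulated trials give 73.6% (A) and 79.3% (B) against the stated 81%. The documents do not give the overlap of death and IMV. From full to no overlap, power runs from 73% to 90%, so 81% is plausible but not uniquely reproducible. Nothing below depends on it.

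**Test for selection.** If a split is fixed before dosing, its expected shares are equal in both arms. The share-weighted average of the two within-group mean differences then equals the overall difference, whatever the baseline risk. A gap therefore means selection. Placebo shares are the weights.

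**NIAID 2 by Day 4.** Let f be the fraction of IMV that starts by Day 4. In A the complement difference is 24 × [0.25(1-f)/(1-0.25f) - 0.125(1-f)/(1-0.125f)], where 24 = 28 - 4. At f = 0.5 this is 24 × (0.125/0.875 - 0.0625/0.9375) = 1.83. With 0 in the NIAID-2 group, the weighted average is 0.125 × 0 + 0.875 × 1.83 = 1.60, against 3.0.

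| f | NIAID-2 share, placebo / LY3127804 | Complement, A [B] | Weighted, A [B] |
|---|---|---|---|
| 30% | 7.5% / 3.75% | +2.4 [+2.6] | +2.2 [+2.4] |
| 50% | 12.5% / 6.25% | +1.8 [+2.2] | +1.6 [+1.9] |
| 70% | 17.5% / 8.75% | +1.2 [+1.7] | +1.0 [+1.4] |
| 100% | 25% / 12.5% | 0 [+0.8] | 0 [+0.6] |

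The 0 in the NIAID-2 group assumes equal death risk per ventilated patient. In A that group's mean is 9 - 10 × death risk. With 50% on placebo (mean 4), 70% on LY3127804 gives 2 (difference -2) and 40% gives 5 (difference +1).

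**Doses, by hand (model A).** Assume half of deaths fall before Day 15, 80% of never-ventilated patients leave before Day 15, and all ventilated survivors receive two doses.

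- Placebo: one-dose (-0.0625 + 0.60 × 28)/0.6625 = 25.26; two-dose (-0.0625 + 0.125 × 9 + 0.15 × 28)/0.3375 = 15.59.
- LY3127804: one-dose (-0.03125 + 0.70 × 28)/0.73125 = 26.76; two-dose (-0.03125 + 0.0625 × 9 + 0.175 × 28)/0.26875 = 20.21.
- Differences +1.50 and +4.62; weighted 0.6625 × 1.50 + 0.3375 × 4.62 = 2.55, against 3.0.
- If LY3127804 also raises early discharge of never-ventilated patients from 80% to 95%: one-dose 26.95 (+1.69), two-dose 12.77 (-2.82); weighted 0.6625 × 1.69 - 0.3375 × 2.82 = +0.17, against an unchanged 3.0.

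**Doses, by simulation.** There are 36 stay assumptions. Never-ventilated stay is lognormal, median 5/7/9/11 days, log-SD 0.4/0.6/0.8. Ventilated survivors' stay is lognormal, median 22, log-SD 0.2/0.3/0.5. Death day is uniform 4-28. Two doses are given if stay is at least 15 days. Each combination has 600,000 patients per arm.

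| Scenario (overall difference) | Two-dose difference, A [B] | Weighted average, A [B] |
|---|---|---|
| Drug changes nothing (0) | 0 | 0 |
| IMV and deaths halved (+3.0) | +0.3 to +4.8 [+0.2 to +4.4] | +1.0 to +2.9 [same] |
| Same, plus 30% shorter stay if never ventilated (+3.0) | -4.1 to +1.6 [-3.1 to +1.6] | -0.2 to +2.0 [0.0 to +2.0] |

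In the second scenario the one-dose difference is +1.1 to +2.0 [+1.2 to +2.1]. The two-dose share in A is 17-45% on placebo and 9-40% on LY3127804. In the third, the two-dose difference in A is negative in 24 of 36 combinations. Shorter stay alone (overall 0, an extreme case) gives -7.4 to -0.2 [-5.9 to -0.1].

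Sensitivity: if patients spared IMV stay longer (median 14 days), the two +3.0 scenarios give two-dose differences of -2.5 to +9.0 [-1.9 to +6.9]. With otherwise unchanged stay, the selection gap in A then shrinks to 0.1-0.6 days.

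**Remdesivir.** No size is claimed. Differences between users and non-users would mostly reflect baseline risk even in a valid subgroup.

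**The case against.** The strongest reply is that little rests on these tables. They are unadjusted supportive splits in a Phase 2 trial, and neither the primary test (SAP 4.12.1) nor the futility rule (SAP 4.16.1) uses them. That stands and limits the severity.

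Several points on size also stand. Apparent harm in the two-dose group needs the added shorter-stay assumption: with ventilation and deaths halved and nothing else, the difference was negative in none of the 36 combinations. No document quantifies a stay reduction, and the direction of the two-dose result depends on assumed stay inputs. If the drug acts only on ventilation starting after Day 4, that split stays valid, and the documents give no onset-of-effect data. The simulation also draws stay separately from ventilator-free days, so about a third of ventilated survivors in A leave hospital before their ventilated days end. Forcing consistency barely matters: the shorter-stay range becomes -3.8 to +1.7, still with 24 negative.

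On the remedy, a caution sentence alone would address much of the misreading. Restricting remdesivir to starts before dosing changes the question from on-study care to baseline care, and the group may be small. Confirmed SARS-CoV-2 status has no stated timing either, though treatment is less likely to affect it.

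None of this makes the splits baseline variables or supplies the missing caution.

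**Conclusion.** The concern holds. Dose number and NIAID 2 within Day 4 are set after randomization, and remdesivir use can be. SAP 4.14 nevertheless plans to analyze the primary endpoint within them without restriction or warning. The contrasts stay valid if treatment leaves membership unchanged. If it acts as hypothesised they can mislead: the weighted within-group difference falls from 3.0 to between 2.2 and 0 days for the Day-4 split in A (2.4 to 0.6 in B), and to between +2.9 and +1.0 for the dose split under the planned effect alone. These sizes rest on assumed stay, timing and death-IMV overlap, and they describe means, whereas the planned test uses ranks. The structural point does not depend on them. The change is worth making because it is cheap, but the trial's main conclusion does not turn on it.

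**What to change.** In SAP 4.14:

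1. **Tables 31 and 32.** Report only the number of patients per arm in each group, or ventilator-free-day summaries by arm with no treatment comparison or test. Add to the section and to both tables: *These groups are formed after randomization; differences between arms within them are not treatment effects.* The sentence is needed in either form, because a by-arm table of counts like that in SAP 4.12.1 would show the same contrast untested.
2. **Table 34.** Define the group as remdesivir started before the first dose of study drug. Include courses already stopped by then, which SAP 4.11 would drop as prior medication. Classify partial dates from the recorded parts where these settle the order, for example an earlier month. Put only starts whose order cannot be determined in a timing-unknown class. Do not apply the SAP 4.3.3 start-date and 23:59 imputation here, since it would assign unknown starts to after dosing.
3. Keep age, sex, BMI and baseline NIAID as planned.

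The cost is some SAP wording, two simpler tables and one changed derivation. Infusion times are recorded, and SAP 4.3.3 already works with medication start dates and times. The downside is less comparative output and a small unknown-timing class. No clinical rule changes.
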